9.3. Variables

All variables are assessed or defined by Flatiron using business rules before and after Palbociclib + AI initiation.

Table 1. List of Variables

| Variable | Operational definition |
|---|---|
| Demographic characteristics | |
| Age | Age at MBC diagnosis, years |
| Age category | <50, 50-64, 65 –74, ≥75 years |
| Gender | Female |
| Race | White, Black, Asian, other, unknown |
| Region of residence | Based on state where the patient resides: Northeast, Midwest, South, West |
| Practice type | Academic, community |
| Insurance type | Commercial, Medicare, Medicaid |
| Menopause status | Pre-/peri-menopausal, postmenopausal, Unknown based on patients age at diagnosis and/or treatment |
| Duration of follow-up | Months from index date to the end of the study or death, whichever came first |
| Clinical characteristics | |
| Type of MBC | De novo MBC (newly diagnosed): Stage 4 at initial BC diagnosis Recurrent MBC: Stages 0-3 at initial BC diagnosis |
| ECOG performance score | ECOG performance at index date, 0, 1,2,3,4 |
| Stage at initial BC diagnosis | Stage I, II, III, IV, unknown/ undocumented |
| Time from initial BC diagnosis to first MBC diagnosis | Months from the date of initial BC diagnosis to the date of metastatic diagnosis |
| ER status | Positive, negative or unknown |
| PR status | Positive, negative or unknown |
| HER2 status | Positive, negative or unknown |
| BRAC status | BRAC 1 and BRAC 2: positive, negative, unknown/unassessed |
| Organ-level metastatic sites | Number of sites; Sites of metastases (bone, lung, liver, brain, distant lymph nodes, other) Visceral vs. non-visceral, bone only |
| De novo metastatic | Yes or no |
| Disease Free Interval (DFI) | Months from the end of adjuvant/neo-adjuvant therapy to the date of disease recurrence <=12 months, 13-24 months, 25-36 months >36 months Unknown |
| Prior neo/adjuvant therapies | Chemotherapy Hormonal therapy Unknown See Table 2 for detail |
| Prior chemotherapy at MBC setting | Chemotherapy (See Table 2 for detail) Unknown |
| Modified Charlson comorbidity index (CCI) | Include Myocardial infarction, Congestive heart failure, Peripheral vascular disease, Cerebrovascular disease, Dementia, Chronic pulmonary disease, Rheumatologic disease, Peptic ulcer disease, liver disease, diabetes, Hemiplegia or paraplegia, renal diseases/impairment, and AIDS/HIV |

| Longitudinal treatment patterns | |
|---|--|

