9.7. Data Analysis

The primary and secondary objectives of the study are to describe patient characteristics, real-world treatment patterns and effectiveness of Palbociclib + AI as initial endocrine based therapy for metastatic breast cancer.

Descriptive analyses: For categorical variables (eg, region, race, and stage at initial diagnosis), data will include the frequency (number of cases) and percentage (%) of total patients observed in each category; for continuous variables (eg, age and time from initial breast cancer diagnosis to metastatic diagnosis), variables will be presented as the mean, standard deviation (SD), median, 25th and 75th percentiles and ranges (minimum and maximum) in some cases. The calculation of percentages will always include the missing category in the case of missing values. Continuous variables may be categorized into intervals, with the distribution of patients (N, %) provided.

Kaplan-Meier curves and landmark analyses will be performed to estimate real-world progression-free survival, overall survival, and time on treatment, time to next line of anti-cancer therapy, and time to first use of chemotherapy. Specifically, landmark time points are 3, 6, 12, 18, 24, 30, and 36 months for rwPFS and rwTR, 0.5, 1, 1.5, 2, 2.5, and 3 years for overall survival, and 3, 6, 12, 18, 24, 30, and 36 months for Time on Treatment with Palbociclib + AI and time to next ant-cancer therapy and to first use of chemotherapy. Ninety-five percent (95%) confidence intervals on the median rwPFS, overall survival, and treatment time will be reported.

The maximum real-world tumor response will be computed for each patient with at least one on-Palbociclib + AI treatment tumor assessment. If a patient has a maximum tumor response of a CR or PR, then the patient will be considered to be a responder. Response rate will be computed using the number of patients with a CR or PR as the numerator and the number of patients with at least 1 on-treatment tumor assessment as the denominator.

[figure not shown]
Subgroup analyses will be conducted according to age, ECOG performance (0, 1, ≥ 2), de novo metastatic, visceral, non-visceral, bone only, disease sites (1, 2, ≥ 3), menopausal status, prior endocrine therapy, prior chemotherapy, prior surgery, prior radiation therapy as appropriate based on availabilities of the data and sample sizes.

The following sensitivity analyses will be performed as appropriate:

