1. A subset of patients receiving Palbociclib+AI in the first-line metastatic setting with at least three prescriptions for Palbociclib will be included.
2. Patients were followed for at least 6 months.

Detailed methodology for summary and statistical analyses of data collected in this study for the primary and secondary objectives is documented herein, following the requirements of the Statistical Analysis Plan (SAP) template; therefore a separate SAP document will not be necessary for these analyses.

CCI

A large rectangular area of the page is completely blacked out, indicating that the content has been redacted. The word 'CCI' is printed in red at the top left corner of this redacted area.

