#### **4.2 TREATMENT WITH A CDK4/6 INHIBITOR AS PART OF A CLINICAL TRIAL SUBGROUPS**

***Subgroup Analyses.*** *Analyses of study measures, as described above, may be repeated focusing alternatively on the following subgroups of interest—sample size permitting—which will be defined on the basis of:*

- Age (year)  
 $\leq 50$ , 51-64, 65-74, 75+
- Race  
White, Black/Asian/Hispanic/Latino
- Disease stage at initial diagnosis  
I or II, III, IV
- ECOG performance status  
0, 1 or 2,  $\geq 1$
- Site of metastasis  
Bone only, Visceral, Non-visceral
- # Metastatic sites

1, 2,  $\geq 3$

- Menopausal status
- ER/PR Status (all patients in data received from Flatiron are HR+)  
ER+/PR-, ER+PR+, ER-/PR+

**Sensitivity Analyses.** IPTW performed under Amendment I indicated an inability to adequately balance baseline variables and clinical characteristics. Propensity score matching (PSM) balanced the two cohorts, but on a reduced number of patients. Therefore, results using PSM and IPTW will be presented.

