### 5.1 EFFICACY/ EFFECTIVENESS ENDPOINT(S)

*All variables are assessed or defined by Flatiron using business rules before and after first line Palbociclib + Letrozole or first line Letrozole alone initiation*

Variable	Operational definition
Demographic characteristics	
Age	Age at MBC diagnosis, years
Age category	$\leq 50$ , 51-64, 65 –74, $\geq 75$ years
Race	White, Black, Asian, other, unknown
Region of residence	Based on state where the patient resides: Northeast, Midwest, South, West
Practice type	Academic, community
Insurance type	Commercial, Medicare, Medicaid
Duration of follow-up	Months from the index date to the date of death, or the data cutoff date, whichever came first.
Clinical characteristics	
Type of MBC	De novo MBC (newly diagnosed): Stage 4 at initial BC diagnosis Recurrent MBC: Stages 0-3 at initial BC diagnosis
ECOG performance score	ECOG performance at index date, 0, 1, 2, 3, 4
Disease stage at initial BC diagnosis	Stage I, II, III, IV, unknown/ undocumented
Time from initial BC diagnosis to first MBC diagnosis	Months from the date of initial BC diagnosis to the date of metastatic diagnosis

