## 6 STATISTICAL METHODOLOGY AND STATISTICAL ANALYSES

This analysis will compare effectiveness outcomes of real-world progression-free survival (rwPFS) as primary outcome and Overall survival (OS) tumor response and time to next line of anti-cancer therapy/chemotherapy as secondary outcomes (depending on the availabilities of the data) in female patients treated with Palbociclib + Letrozole as first line MBC therapy versus Letrozole alone.

Means, medians, and standard deviations will be provided for continuous variables. Counts and percentages will be provided for dichotomous and polychotomous variables. Appropriate tests (t-tests and chi-square tests) will be provided for baseline demographic and clinical characteristics.

Inverse probability treatment weighting (IPTW) will be used to balance baseline demographic and clinical characteristics and to adjust analyses for differences in observed potential confounders between the two study cohorts. The balance in important prognostic baseline characteristics will be assessed using a standardized differences approach, with values  $\geq 0.10$  indicating a non-negligible imbalance.

Propensity scores for use in IPTW will be calculated using a multivariable logistic regression model based on the following proposed baseline covariates such as age, race, practice type, type of MBC, ECOG performance score, disease stage at diagnosis (I–IV or unknown/undocumented), number of disease sites at MBC diagnosis (1, 2,  $\geq 3$ ), bone-only metastases, visceral metastases, and individual Charlson comorbidities, depending on data availability. Stabilized weights based on the propensity scores will be computed. The final list of variables to be used in the propensity score model will be discussed and determined during analysis development, after reviewing pre-matched descriptive tables. The selection of covariates for analysis will be based on the study team's clinical judgment.

The Kaplan-Meier method adjusted for weighted stabilized IPTW scores and 95% confidence intervals (CIs) will be used to estimate median rwPFS. Cox proportional hazards analyses adjusted for weighted stabilized IPTW scores will be used to estimate hazard ratios and 95% CIs for PFS.

The Kaplan-Meier method and 95% CIs will be used to estimate:

- proportions of patients surviving by cohort at follow-up years 1 through 4.

The Kaplan-Meier method adjusted for weighted stabilized IPTW scores and 95% CIs will be used to estimate:

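### The ECOG subgroups in SAP 4.2 (0; 1 or 2; ≥1) overlap and do not match the protocol's disjoint groups (0, 1, ≥2)

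*Protocol*

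**What the plan says.** Protocol 9.7 (Data Analysis) says "Subgroup analyses will be conducted according to age, ECOG performance (0, 1, ≥ 2", followed by further factors, subject to data availability and sample size. The score itself is defined in Protocol 9.3, Table 1, as "ECOG performance at index date, 0, 1,2,3,4" and in SAP 5.1 as "ECOG performance at index date, 0, 1, 2, 3, 4".

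SAP 4.2 (Subgroups) groups ECOG as 0, 1 or 2, and ≥1. It gives no reason for departing from the protocol and does not say that ≥1 is a pooled alternative to 1 or 2. These analyses are optional: they "may be repeated focusing alternatively on the following subgroups of interest", if sample size allows.

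The two documents cover largely different analyses. For the primary and secondary objectives, Protocol 9.7 says the methods are set out there and "therefore a separate SAP document will not be necessary for these analyses". SAP section 6 describes a comparison "in female patients treated with Palbociclib + Letrozole as first line MBC therapy versus Letrozole alone".

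On age, Protocol Table 1 has "<50, 50-64, 65 –74, ≥75 years". SAP 4.2 and 5.1 both put the first cut one year higher: ≤50, then 51-64.

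**The concern.** A list of ECOG subgroups is normally read as a partition: each patient sits in one row, and the rows together describe how the result varies with performance status. The SAP list cannot be read that way, because its second row lies wholly inside its third. If it is programmed as printed, the subgroup output will show two rows built mostly from the same patients, and a reader may take their agreement as independent support.

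The SAP rows also cannot be set beside the protocol's. The protocol separates ECOG 1 from ECOG ≥2; the SAP never does. Someone wanting to know whether the comparison with letrozole alone looks similar in patients with ECOG ≥2 would find no row that answers the question.

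**Working it through.** No sample size, power or alpha figure bears on this point, so there is no stated number to reproduce. The check is to assign each possible score to every group that contains it.

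**Inputs.** Scores 0 to 4 (Protocol Table 1; SAP 5.1). Protocol groups 0, 1, ≥2 (Protocol 9.7). SAP groups 0; 1 or 2; ≥1 (SAP 4.2).

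| ECOG score | Protocol 9.7 row | SAP 4.2 row(s) |
|---|---|---|
| 0 | 0 | 0 |
| 1 | 1 | 1 or 2; ≥1 |
| 2 | ≥2 | 1 or 2; ≥1 |
| 3 | ≥2 | ≥1 |
| 4 | ≥2 | ≥1 |

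**Disjointness.** Under the protocol each score falls in exactly one row. Under the SAP, scores 1 and 2 fall in two rows. As sets, {1, 2} is contained in {1, 2, 3, 4}, and the difference between them is {3, 4}.

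**Row totals.** Let p0, p12 and p34 be the shares of patients with scores 0, 1-2 and 3-4 among those with a recorded score, so that p0 + p12 + p34 = 1. The SAP rows sum to p0 + p12 + (p12 + p34) = 1 + p12. The excess over 100% is exactly the share with ECOG 1-2. The part of the ≥1 row that repeats the row above it is p12 / (p12 + p34), which reaches 1 if nobody scores 3 or 4. The documents give no ECOG distribution, so these stay as formulas.

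**Can the protocol's groups be rebuilt from the SAP rows?** Every SAP row contains both of scores 1 and 2 or neither, so no combination of rows can separate them. Unions, intersections and differences of {0}, {1, 2} and {1, 2, 3, 4} give only the empty set, {0}, {1, 2}, {3, 4}, {0, 1, 2}, {0, 3, 4}, {1, 2, 3, 4} and {0, 1, 2, 3, 4}. Neither {1} nor {2, 3, 4} is among them.

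**Reach.** The SAP 4.2 grouping does not feed the main comparison. SAP section 6 lists the ECOG performance score as a proposed propensity-score covariate, SAP 5.1 defines that score as 0 to 4, and nothing in section 6 adopts the 4.2 groups.

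**Age.** With age in whole years, the protocol puts age 50 in its second band and the SAP puts it in its first. No other age changes band. Protocol 9.7 itself gives no age cut-points for its subgroup analyses; the bands come from Table 1.

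**The case against.** The best defence is scope. The secondary objective that names ECOG concerns palbociclib plus AI, and Protocol 9.7 governs it without a separate SAP. A reader might infer from the SAP list that ECOG ≥2 is never isolated anywhere in the study, or that the secondary objective is compromised. The documents do not support that: 0, 1, ≥2 still applies there. The separation is not perfect, since SAP 5.1 and 6.1 also cover some palbociclib plus AI outcomes such as time to next line and time to chemotherapy. It is still enough to limit the consequence.

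A reader might also infer that patients are counted twice in an estimate, or that a test across ECOG subgroups is invalid. Neither follows. Each SAP subgroup is a separate, optional repeat of the analysis, so overlap means membership in two rows and not double weight in one result. Neither document plans an interaction or between-subgroup test.

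The line may also be a slip. With ≥3 in place of ≥1 it would partition scores 0 to 4 exactly. That is plausible but cannot be confirmed, and the line is unusable as a set of categories until it is corrected. If ≥1 was meant as an alternative pooling against 0, the SAP does not say so, and ECOG ≥2 would still have no row.

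Finally, nested subgroups are not unknown here: bone only may sit inside non-visceral in both documents. There, however, the two documents list the same groups. For ECOG they do not.

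**Conclusion.** The point holds as a defect in one line of SAP 4.2. The ECOG rows overlap under any distribution of scores, and the protocol's ECOG 1 and ECOG ≥2 groups cannot be rebuilt from them. This follows from the categories and the 0 to 4 scale alone. How nearly the last two rows coincide depends on how many patients score 3 or 4, which the documents do not say; they are near-duplicates if such patients are few.

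The size is modest. Only the SAP's optional subgroup reporting is affected, mainly for palbociclib plus letrozole against letrozole alone. The overall rwPFS and OS results stand, as do the protocol's own subgroup analyses. The age-band difference is a minor matter of consistency.

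**What to change.** In SAP 4.2, replace the ECOG line with the protocol's groups: 0, 1, ≥2. If a different grouping was intended, for example 0, 1-2, ≥3, state it as a disjoint set and give the reason for departing from the protocol. SAP section 1 says Amendment 3.0 was prepared after the data were transferred and locked, so the correction should be dated and should say whether any ECOG subgroup results had already been produced.

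At the same time, use one set of age bands in both documents, or note why they differ.

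The cost is a line or two of wording and a recode of variables already in the data set; no new data are needed. The drawback is that the highest-ECOG row may be small and its interval wide. Both documents already make subgroup analyses conditional on sample size, so that can be handled by reporting the row with its count or by saying why it was not analysed.

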9. RESEARCH METHODS

9.1. Study Design

A retrospective cohort study of treatment patterns and effectiveness of Palbociclib + AI as initial endocrine based therapy during the period February/3/2015 through August/31/2018 (or 3 months prior to study cut-off date) for MBC will be conducted utilizing secondary de-identified Flatiron Healthcare Analytic data in the United States. This study design is selected to meet the study objectives with consideration of feasibility and availability and validity of exiting database.

- **Index date:** the date of first prescription for + AI between February 3, 2015 and August 31, 2018 (or 3 months prior to study cut-off date).
- **Observation period:** February 3, 2015 – study cut-off date.
- **Follow-up:** Patients will be followed from the index date to the end of the study (study cut-off date) or death, whichever came first.
 - **Primary endpoints**
 - RwPFS.
 - **Secondary endpoints**
 - OS.
 - RwTR.
 - Response rate.
 - Real-world duration of treatment (rwDOT).
 - Time from index date to next line of anti-cancer therapy and time to first use of chemotherapy.

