9.2.1. Inclusion Criteria

Patients must meet all the following inclusion criteria to be eligible for inclusion in the study:

1. Female sex.
2. At least 18 years old at MBC diagnosis.
3. Diagnosis of MBC at any point in patient history.
 - a. ICD-9 (174.x, 175.x) or ICD-10 (C50.xx) diagnosis of BC.
 - b. Confirmation of metastatic disease.
 - c. At least 2 document clinical visits.
- d. Evidence of stage IV or recurrent MBC with a metastatic diagnosis date on or after 2011, as confirmed by unstructured clinical documents.
4. HR+/HER2-.
 - a. HR+: ER+ or PR+ test before or up to 60 days after MBC diagnosis.
 - b. HER2-: any HER2 negative test and the absence of a positive test (IHC positive 3+, FISH positive/amplified, Positive NOS) before or up to 60 days after MBC diagnosis.
5. Palbociclib + AI or letrozole alone as initial endocrine based therapy (ie, first line therapy) for MBC during the period from February/2015 through August/31/2018 (or 3 months prior to study cut-off date) to allow for a possible minimum follow-up time of 90 days until the study cut-off date. AI was administered within (\pm) 28 days of Palbociclib index date.

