| Lines of therapy | Lines of therapy in the metastatic setting are assigned by Flatiron to evaluate systemic treatment on or after the MBC date |
| Initial prescribed dose | Palbociclib: 125mg, 100mg, 75mg using |
| Dose adjustment | Dose strength other than initial/previous prescription |
| Type of the first dose change | Dose reduction 125mg to 100mg, 125mg to 75mg, 100mg to 75mg Dose increase 75mg to 100mg, 100mg to 125mg, 75 mg to 125 mg |
| Time to the first dose change | Days from index date to first dose change |
| Number of dose adjustment | Number of dose reduction and number of dose increase over the calendar time (quarter since February 2015) and over treatment cycle since index date |
| Reasons for dose adjustment | As categorized by Flatiron |
| Reasons for discontinuation | Disease progress, toxicity, financial, patient request, other |
| Duration of treatment | Days from index prescription order date to end of treatment |
| Combination endocrine partner | Letrozole, Anastrozole, Exemestane |
| Concomitant LHRH Agonists | Goserelin (Zoladex), Histrelin (Vantas), Leuprolide (Eligard, Lupron), Triptorelin (Trelstar) |
| Other concomitant anti-cancer therapies | Chemotherapy (See Table 2 for detail) |
| Effectiveness outcomes | |
| Real-world PFS (rwPFS) | Months from index date to death or disease progression (growth or worsening in the disease concluded by the treating clinician based on radiology, laboratory evidence, pathology, or clinical assessment) whichever came first. If patients did not die or have disease progression, they were censored at the date of initiation of next line of therapy for patients with two or more lines of therapy or their last visit date during the study period for patients with only one line of therapy |
| Overall survival (OS) | Months from index date to the date of death. Patients who did not die period are censored at the time of data cut-off |

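### Both sensitivity analyses in Protocol 9.7 select patients on what happens after index while rwPFS and OS still run from index; as written, the 6-month rule makes 0.5-year OS 100%

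*Protocol*

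**What the plan says.** Protocol 9.7 lists two sensitivity analyses in its visible text, to be done as appropriate and tied to no particular endpoint.

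- **Analysis 1:** "A subset of patients receiving Palbociclib+AI in the first-line metastatic setting with at least three prescriptions for Palbociclib will be included".
- **Analysis 2:** "Patients were followed for at least 6 months". That is the whole definition.

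The terms they depend on are defined elsewhere in the Protocol:

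- **Follow-up**, Section 9.1: "Patients will be followed from the index date to the end of the study (study cut-off date) or death, whichever came first". Table 1 in Section 9.3 repeats this for duration of follow-up: "Months from index date to the end of the study or death, whichever came first".
- **OS**, Table 1: "Months from index date to the date of death", with survivors censored at data cut-off.
- **rwPFS**, Table 1: "Months from index date to death or disease progression", whichever is first.
- **OS reading times**, Section 9.7: "0.5, 1, 1.5, 2, 2.5, and 3 years for overall survival".

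Neither sensitivity analysis sets a new time origin or delayed entry. The landmark times in Section 9.7 are only points at which the curves are read. The SAP's sensitivity text (Section 4.2) concerns propensity-score matching and weighting and does not redefine these two rules.

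**The concern.** Whether a patient enters either subset depends on events after time zero, yet the survival clock still starts at time zero. The time before a patient can qualify is then time in which the patient could not have died (immortal time).

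For analysis 2 the qualifying condition is the OS outcome itself: surviving 6 months. For analysis 1 it is reaching a third prescription. That requires survival to that date and tends to remove patients who progressed or stopped early.

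A sensitivity analysis is meant to show whether the main result depends on a questionable choice. If agreement with, or improvement on, the main OS and rwPFS results is partly built in by the selection, the comparison says little about robustness. A reported six-month OS of 100% would also mislead a reader who does not trace it to the filter.

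**Working it through.** **Analysis 2: the definitional result.** Let D be time from index to death and C time from index to cut-off. Follow-up is F = min(D, C), and the rule keeps patients with F ≥ 6 months. This removes two groups:

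1. C < 6: patients indexed late. This is fixed at index and harmless.
2. D < 6: patients who died early. This is the outcome.

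Among those kept, no death and no OS censoring occurs before month 6. Hence S_kept(t) = 1 up to month 6 and S_kept(t) = S(t)/S(6) afterwards. The 0.5-year figure needs no assumption about mortality. (A death at exactly 6 months is an edge case. The SAP notes that death dates are given only to the month, but the same date drives both the filter and OS.)

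**Analysis 2: size for OS.** The documents give no OS figure, so 24-month OS of 70% and 85% is assumed. The 1,367 is the palbociclib + AI count in Protocol 9.5.

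- Constant hazard: S(t) = S24^(t/24)
- Rising hazard (Weibull shape 1.5): S(t) = S24^((t/24)^1.5)
- Dropped = 1 − S(6); 12-month OS reads S(12)/S(6)

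| Model | S24 | Dropped | Of 1,367 | True 12-month OS | Reads |
|---|---|---|---|---|---|
| Constant | 0.70 | 8.5% | 117 | 83.7% | 91.5% |
| Constant | 0.85 | 4.0% | 54 | 92.2% | 96.0% |
| Weibull 1.5 | 0.70 | 4.4% | 60 | 88.2% | 92.2% |
| Weibull 1.5 | 0.85 | 2.0% | 27 | 94.4% | 96.4% |

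The counts assume that all 1,367 have 6 months of potential follow-up.

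**Analysis 2: size for rwPFS.** Assume an illness-death model with exponential times: median rwPFS 24.8 months (the PALOMA-2 value cited in Protocol 7), so h = ln 2/24.8 = 0.02795 per month; a share p of rwPFS events that are deaths, 5-20%; and median post-progression survival M of 12-36 months, so r = ln 2/M.

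- P(rwPFS event before month 6) = 1 − e^(−6h) = 0.1544
- P(progression and then death, both before month 6, if the rwPFS event is a progression) = 1 − (r·e^(−6h) − h·e^(−6r))/(r − h) = 0.0088 for M = 36 and 0.0245 for M = 12
- Dropped, lowest: 0.05 × 0.1544 + 0.95 × 0.0088 = 0.016
- Dropped, highest: 0.20 × 0.1544 + 0.80 × 0.0245 = 0.0505
- Early progressors kept: 1 − 0.0245/0.1544 = 84% to 1 − 0.0088/0.1544 = 94%
- Median rwPFS reads 24.8 − ln(1 − dropped)/h = 25.4 to about 26.7 months
- 12-month OS by simulation of the same model: 95.5% reads 97.1% in the mildest case and 87.6% reads 92.3% in the strongest, that is 1.6 to 4.7 points higher

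So rwPFS is shifted but not forced to 100% at month 6, because most early progressors are alive then and stay in.

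**Analysis 1.** The documents give no prescription interval; assume the third prescription falls near day 56, m = 56/30.44 = 1.84 months. The share with an rwPFS event by then is 1 − e^(−0.02795 × 1.84) = 0.050. If a fraction q of these events prevents the third prescription, the share excluded is 0.050q and the median reads −ln(0.5 × (1 − 0.050q))/h:

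| q | Excluded | Median (true 24.8) |
|---|---|---|
| 0.25 | 1.3% | 25.3 |
| 0.50 | 2.5% | 25.7 |
| 1.00 | 5.0% | 26.6 |

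The direction can reverse. If no early event prevents the third prescription and the rule instead drops 10% of patients who have half the hazard of the rest, the median falls to 23.3 months.

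**The case against.** **The authors may have meant potential follow-up.** The sentence is a fragment, and inclusion criterion 5 contains a calendar rule of that kind. If so, the problem with analysis 2 disappears. But that criterion says so: "to allow for a possible minimum follow-up time of 90 days until the study cut-off date". SAP 2.1 likewise qualifies its 3 months as potential. The 6-month sentence has no such qualifier, and follow-up is defined twice as ending at death. A third reading, follow-up to the last visit, would not help: a patient who dies before month 6 has no later visit and is still dropped.

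**OS is not named.** The analyses are done as appropriate and for no stated endpoint, so the 100% figure appears only if OS is rerun at 0.5 year. True, but nothing limits them to other endpoints, and rwPFS, the primary endpoint, is also affected.

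**Analysis 1 is the weaker part.** This stands. An origin is stated, namely index; the fault is that it is kept after a post-index selection. The restriction is reasonable in itself, since Protocol 9.9 notes that a prescription does not show a fill. The subset is openly described, and the illustrations fall on both sides of 24.8 months.

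**The size is modest and rests on assumptions.** This also stands. Constant hazard gives the largest figures in the OS table. Under uniform indexing to 31 August 2018 and a 30 November 2018 cut-off, about 7% (3 of 42.9 months) lack 6 months of potential follow-up, which lowers the counts slightly.

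**Other checks exist.** The SAP has matching alongside weighting, and alternative gap lengths for line of therapy. These answer different questions. A redacted block follows the list in Protocol 9.7, so only the visible text can be judged.

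**Conclusion.** The concern holds. On the Protocol's own definitions, analysis 2 removes every death before month 6, and 0.5-year OS is 100% by construction; this part needs no outside assumption. The inflation of later estimates is illustrative: about 2 to 8 percentage points on 12-month OS across the survival models tried, and about 0.6 to 1.9 months on a 24.8-month median rwPFS. For analysis 1, guaranteed survival to the third prescription is certain, while the net direction is probably favourable but not assured.

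The main analysis is untouched. The consequence is that the two sensitivity analyses visible in Protocol 9.7 cannot serve as a fair test of the OS and rwPFS results. This should be corrected, but it does not threaten the study.

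**What to change.** **Analysis 2.** Define the subset by potential follow-up: patients whose index date is at least 6 months before the data cut-off, all retained whatever happens afterwards. In a simulation with 6-month mortality set at 2%, 5% or 10%, this rule returned 0.5-year OS of 98%, 95% and 90% and a median rwPFS of about 24.8 months, the same as in all patients.

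**Analysis 1.** State how time is handled after the selection. Either start the clock at the third palbociclib prescription, among patients alive then (OS) or alive and progression-free then (rwPFS), or keep index as origin with delayed entry at that date. Label the results as conditional on reaching the third prescription.

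**Cost.** Two sentences in Protocol 9.7, a changed filter and an entry time in the programs, and slightly fewer events and a conditional estimand for analysis 1. No new data. SAP Section 1 says the primary and most secondary analyses had already been run after database lock, so if these two were among them they need a rerun, with the change reported as made after the fact.
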